Title: Modulating brain activity to improve goal-directed physical activity in older adults

Date: 10-11-2022

Principal Investigator: [name]. [contact]

Organization: Institute for Aging Research Address: [name]

[contact]

Sponsor: National Institute on Aging - NIA/NIH: [name]

Advarra Protocol #Pro00044372

HSL IRB #: IRB-2019-26

Research Site: Institute for Aging Research Address: [name]

[contact]

Study Team:

[name]

[name].

[name]. at University of Pittsburgh

This protocol was prepared to meet the IRB requirements for a protocol. A prior application from Cayuse was submitted to transfer the study to Advarra for initial approval.

Purpose

Although the majority of older adults are aware of the compelling evidence that regular exercise is critical to the maintenance of health into old age, most do not meet recommendations for daily exercise. This lack of engagement in ‘goal-directed’ physical activity stems from numerous interrelated factors including lack of motivation, depressed mood, and cognitive “executive” impairments that diminish one’s ability to regulate behavior over time. Intriguingly, each of these factors has been linked to the function of brain networks that include the left dorsolateral prefrontal cortex (dlPFC). Transcranial direct current stimulation (tDCS) is a noninvasive and safe means of modulating the excitability of specific brain regions and their connected neural networks. tDCS designed to facilitate the excitability of the left dlPFC has been shown to improve motivation, mood, and multiple aspects of executive function in healthy adults. We thus hypothesize that tDCS holds promise to increase goal-directed physical activity in older adults.

We aim to conduct a pilot randomized controlled trial on the feasibility and effects of a 2-week, 10-session tDCS intervention targeting the left dlPFC on physical activity and community mobility, over a two-month period following the setting of a personalized physical activity goal, in relatively physically-inactive older adults without overt illness or disease.

Background

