Participants will complete 10 twenty minute brain stimulation sessions (Monday-Friday) over the next two weeks.

tDCS intervention: Similar to our preliminary study, this intervention will consist of 10, 20-minute sessions delivered on Monday-Friday over two weeks. Stimulation will be delivered using the Startim-8™ device and software (Neuroelectrics Corp, Cambridge MA), which enables custom amounts of current to be delivered through an array of up to eight Pi™ gel Ag/AgCl electrodes placed on the scalp according to 10-20 EEG convention. This system also enables the blinding of study staff and participants to stimulation type. At the end of the first session and every other session thereafter, participants will complete a side effects questionnaire.⁵¹ A blinding efficacy questionnaire will also be completed after the final session, on which participants state whether they believe they received tDCS or sham and their confidence in this belief.

Real tDCS: Similar to our preliminary studies, tDCS will be delivered via six gel electrodes with placement and current parameters optimized based on a standard brain to maximize the average normal component of the generated electric field over the left dlPFC. Current delivered by anyone electrode will never exceed 2.0 mA; the total amount of current from all electrodes will not exceed 4 mA. Each 20-minute session will begin and end with a 60-second ramp up/down of current amplitude to maximize comfort.

Sham stimulation: An 'active' sham will be used in which very low-level currents are transferred between the same electrodes used in the active condition throughout the 20-minute session. However, currents will be designed to mimic the cutaneous sensations induced by tDCS yet not significantly influence cortical tissue. This approach effectively blinds participants and operators to stimulation condition and does not affect functional outcomes.⁵²

Visit 14: Follow-Up Assessment (1.5 hours); Participant's Housing site

Follow-up assessment, as described above in Visit 2, will be completed immediately after and 2 weeks after the tDCS intervention.

Visit 15, 16 and 17: Follow-up Personalized Counseling visits (30 minutes); Participant's Housing site

Three bi-weekly in-person counseling sessions will be completed after the tDCS intervention.

Visit 18: Final Assessment visit (1.5 hours); Participant's Housing site

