Assessment of feasibility endpoints will be based on sample computations, including the screened to enrolled ratio, retention rate, assurance of blinding, and safety assessment (see above). Adverse events (AE) will be organized according to the MedDRA classification system and reported in each DSMB communication both by MedDRA System Organ Class (SOC) and overall. Both the number of individuals with one or more of AEs within each SOC, as well as the total count of all AEs within each SOC, will be reported. These will be accompanied by point and 95% confidence interval estimates of the proportion of individuals who would experience AEs and the total count of AEs per person-time within each SOC, respectively. The latter computation will acknowledge clustering at the level of the participant by using generalized estimating equations (GEE) in estimation with robust variance estimates used for computing confidence intervals.

We will use variance decomposition to generate estimates of within and between-individual variation in functional outcomes that would potentially be used in a subsequent trial (see above), along with confidence interval estimates for said variance measures, in order to assist in planning of the subsequent study. We will also conduct an exploratory analysis of the mean change in these endpoints using mixed-effects linear regression of all time points, with a random effect included at the participant level in acknowledgement of serial correlation of repeated measures. Dependent variables will be the change in outcomes related to average daily activity from baseline to the six-week post-tDCS follow-up period, as well as the change in laboratory-based functional outcomes from baseline to each planned follow-up visit.

Feasibility outcomes:

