The proposed sample size was motivated by our experience in similar pilot studies, the need to develop a sufficiently detailed profile of the background population and convincing demonstration of the feasibility of our protocols, the anticipated drop-out rate, and the need to make resource and sample size estimations for the subsequent trial. We anticipate, based on prior work, that we will screen between 5 and 15 individuals for each participant enrolled. Enrollment of 32 individuals will allow us to determine within 1 individual the expected number of participants screened to enrolled in the subsequent trial using an 80% confidence interval; similarly, we will be able by the same method to estimate the probability a given participant will complete intervention to within 0.10.

Functional outcomes:

Assuming type-I error probability = 0.05 and cumulative attrition and missingness approximately = 20% (i.e.

evaluable data on 26 participants with complete data, the design will obtain 90% power to detect standardized differences [ratio of mean within-participant difference on endpoints to the standard deviation (SD) of same] of at least 0.41, and 80% power to detect effects of 0.36 or greater.

Our primary functional endpoint is habitual physical activity defined as average daily step counts derived from a FitBit wristband. As no prior study has investigated the change in total steps per week as a result of this type of intervention, we estimate the SD of the intervention-attributable change based on prior data on changes in weekly step counts in other conditions. Given that a prior study of pulmonary rehabilitation demonstrated a SD of 150 steps per week,⁸⁴ we will have 90% power to detect changes as small as 62 steps per week, and 80% power to detect 54 steps per week.

The GPS data will be analyzed by the team at the University of Pittsburgh. The GPS data were downloaded to a secure computer and saved with only the study ID number. Our team will upload the GPS data to the secure server at the University of Pittsburgh. No other identifiable information will be provided to the team at the University of Pittsburgh.

Data Storage and Confidentiality

Data Storage

All data collected for analysis will be de-identified and assigned a unique study number. Data collection forms will be kept in a locked file cabinet in the office of the PI at Hebrew SeniorLife. Data will be entered and stored on a password-protected secure server at HebrewSeniorLife.

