**Study Title: Modulating brain activity to improve goal-directed physical activity in older adults**

**NCIT number: NCT04278560**

**Date of the document: 10/27/2023**

### **Statistical Methods**

Overall approach: Exploratory analyses will be used to assess outcomes distributions, and any necessary transformations (e.g., to combat significant skew) will be performed prior to estimation of mean treatment effects. Said estimation will use mixed effects linear regression of post-intervention within three days after the last brain stimulation session and again within three days after the last behavior session, with random intercepts and slopes to account for serial correlation in repeated measurements on individuals. Models will control for baseline outcomes in analysis of covariance.

Two-way repeated-measures ANOVA will be used to examine the effect of intervention on primary and secondary functional outcomes. The effect of the 10-session tDCS intervention on the primary functional outcome (daily step count) will be analyzed with a two-way repeated-measures ANOVA. The dependent variable will be *the change in average daily step count from the two-week baseline to each two-week study period of the behavioral intervention*. Model effects included group (tDCS, sham), time (two-week period), and their interaction. The effect of intervention on secondary functional outcomes, which will be collected at baseline, after the two-week brain stimulation intervention, and after the behavioral intervention. Dependent variables will be *the changes in each functional outcome from baseline to each follow-up visit*. The model's effects included group (tDCS, sham), time (post-stim, final) and their interaction.

The feasibility outcomes are the completion rates for the brain stimulation sessions and the behavior sessions, respectively. We will use independent t-tests to examine the differences between two study arms.

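### The SAP's only stated analysis of session completion is a between-arm t-test, which does not estimate how high completion is; a defined rate with a confidence interval would

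*SAP*

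**What the plan says.** The SAP (Statistical Methods, last paragraph) states: "The feasibility outcomes are the completion rates for the brain stimulation sessions and the behavior sessions, respectively". The next sentence gives the only analysis: "We will use independent t-tests to examine the differences between two study arms". It does not say whether a completion rate is a fraction of sessions per participant or the share of participants who complete, and it states no interval or denominator.

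The Protocol's Purpose section describes the aim: "We aim to conduct a pilot randomized controlled trial on the feasibility and effects of a 2-week, 10-session tDCS intervention". Its Data Analysis section says: "Assessment of feasibility endpoints will be based on sample computations, including the screened to enrolled ratio, retention rate, assurance of blinding, and safety assessment". Under Feasibility outcomes, the reasons for the sample size include "the need to make resource and sample size estimations for the subsequent trial". The same paragraph promises to determine, within one individual, "the expected number of participants screened to enrolled in the subsequent trial using an 80% confidence interval", and adds that "we will be able by the same method to estimate the probability a given participant will complete intervention to within 0.10".

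On the number of sessions, the Protocol says of stimulation that "this intervention will consist of 10, 20-minute sessions delivered on Monday-Friday over two weeks". It describes in-person counseling at Visits 3, 15, 16 and 17, plus telephone counseling. The SAP neither repeats nor withdraws the Protocol's feasibility estimates.

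**The concern.** A pilot that reports on feasibility has to say how well participants kept to the sessions and how uncertain that figure is. A p-value for the difference between arms answers another question: whether real stimulation drives people away more, or less, than sham. That is worth asking, but two arms can have the same completion and both be poor. At this sample size, two arms can also differ materially without the test showing it.

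At stake is the planning value of the two outcomes that the SAP itself names. If the report follows the SAP literally, the stated inference for each session type is a single t-test, and whoever plans the next trial must build the uncertainty in the completion level from whatever summaries are printed.

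**Working it through.** **1. The Protocol's own figure.** Under Feasibility outcomes, a participant's probability of completing is to be estimated to within 0.10 with an 80% interval. Inputs: n = 32; completion p = 0.80, from the Protocol's attrition of about 20%; z = 1.2816 for 80% confidence. Half-width = z × √(p(1−p)/n) = 1.2816 × √(0.16/32) = 0.091. The figure reproduces, and holds for p of about 0.735 or more; at p = 0.50 the half-width is 0.113. So an interval for a yes/no completion probability is planned and is about as precise as stated. Neither document gives a figure for the fraction of sessions completed, so there is nothing to reproduce for that.

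**2. What the t-test can detect.** Two-sided 5%, 16 per arm, 30 degrees of freedom. By the noncentral t distribution, 80% power needs a difference of about 1.02 SD. (The normal approximation (1.96 + 0.8416) × √(2/16) gives 0.99.)

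**3. In percentage points, by assumption.** The documents give no between-participant spread for attendance. Assume beta-binomial attendance with mean p, m sessions and concentration k, from 0.5 (misses concentrated in a few people) to 10 (misses spread out). The variance of a participant's fraction is p(1−p)/m × [1 + (m−1)/(k+1)]. For m = 10 and p = 0.90 the SD is 0.251, 0.171 and 0.128 at k = 0.5, 3 and 10.

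Hand check at k = 0.5, 90% against 80%: variances 0.063 and 0.112; standard error √((0.063 + 0.112)/16) = 0.105; 0.10/0.105 = 0.956; power about Φ(0.956 − 1.96) = 0.16. Simulation gives 0.15.

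| Higher arm 90%, 16 per arm | k = 0.5 | k = 3 | k = 10 |
|---|---|---|---|
| 10 stimulation sessions: power for 90% v 80% | 0.15 | 0.28 | 0.45 |
| Gap for 80% power (points) | 36 | 23 | 16 |
| 4 in-person counseling sessions: power for 90% v 80% | 0.14 | 0.22 | 0.28 |
| Gap for 80% power (points) | 37 | 27 | 23 |

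The count of four uses Visits 3, 15, 16 and 17 and leaves out telephone calls. The Protocol numbers its visits differently under Payment to Participants, and calls Visit 15 the final study visit in its Visit 3 section, so the count is itself an assumption.

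**4. What an interval for the level would give.** Same model, 90% completion of 10 stimulation sessions, nominal 80% confidence. The interval is Clopper-Pearson on an effective sample size: p(1−p) divided by the between-participant variance of the mean, kept between the number of participants and the number of sessions, and set to the number of participants if that variance is zero.

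| Mean half-width (points) | k = 0.5 | k = 3 | k = 10 |
|---|---|---|---|
| All 32 | 6.5 | 4.3 | 3.1 |
| One arm of 16 | 9.3 | 6.1 | 4.5 |

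Simulated coverage was 0.81 to 0.96 over 10 and 4 sessions, n of 16 and 32, and mean completion of 60% to 98%. A plain t interval on participant fractions is not safe near the ceiling: with 16 participants, 98% completion and k = 0.5 it covered only about 0.41.

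**5. Full attendance.** If every session is attended, both variances are zero and the t statistic is 0/0. The exact 80% lower limit, with the participant as the unit, is 0.10^(1/n): 0.10^(1/32) = 0.931 overall and 0.10^(1/16) = 0.866 per arm.

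**The case against.** The strongest reply is that the Protocol already covers completion. The SAP does not define completion rate; if it means the share of participants who complete, the planned 80% interval largely covers stimulation. That stands. A t-test fits a per-participant fraction better, but does not settle the meaning. Even on the yes/no reading, the Protocol's statement does not separate behavior sessions from stimulation sessions.

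A second reply is that little is lost. Reporting the rates is implied, the Protocol's list of feasibility endpoints is worded as open-ended, and a normal report of a t-test prints means, SDs and numbers from which an approximate interval can be built. This is why the point is minor.

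Third, the tables in steps 3 and 4 must not be set against each other as like with like. One uses an 80%-power criterion at two-sided 5%, the other an 80% half-width. On the same footing, an 80% interval for the arm difference (90% in both arms, 10 sessions) has a half-width of about 5.8 to 11.2 points, under twice that of the overall level. The case for the interval is that it answers the planning question, not that it is far more precise.

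A reader might infer that the trial plans no interval for any feasibility outcome, or that comparing completion between arms is a mistake. The documents support neither. The Protocol plans estimates for screening, retention, blinding and safety, with 80% intervals for the screening ratio and participant completion, and differential completion is a fair question.

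**Conclusion.** The point holds in a limited form. For the two outcomes that the SAP names, the only stated analysis does not estimate the level of completion, and neither document plans an interval for a per-participant session fraction or for behavior sessions. Three facts need no assumption about attendance: the t-test has 80% power only for about 1.02 SD at 16 per arm, it cannot be computed at full attendance, and it is not an estimate of the level. The figures in percentage points rest on the assumed beta-binomial range, because the documents give no session-level spread. An alternative assumption of an SD from 0.10 to 0.30 gives the same picture: at SD 0.20, power for a 10-point gap is 29% (normal approximation), while a 95% interval for the overall level has a half-width of 0.072.

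Severity is minor. No data are lost, and neither the step-count outcome nor safety is affected.

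**What to change.** In the SAP:

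- Define completion rate, either as the fraction of scheduled sessions per participant or as yes/no, and state the denominator for each session type. Say whether telephone calls count as behavior sessions.
- Make the main feasibility analysis the estimated completion rate for stimulation and for behavior sessions, overall and by arm. Give each a confidence interval that treats the participant as the unit and stays valid near 100%. An 80% level would match the Protocol's feasibility statement; another level is acceptable if stated (the Protocol uses 95% for adverse events). The effective-sample-size Clopper-Pearson interval is one option, not a requirement.
- Keep the difference between arms as a secondary estimate with its own confidence interval.

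The cost is a few sentences in the SAP and a little analysis code. No new data are needed. The interval used here as an example is slightly conservative.
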